6.1.2 Treatment duration

The duration of treatment with eltrombopag will be based on the reasons described below and other reasons for early withdrawal ([Section 7.2.3.17.2.3.1](#)):

- If no partial or complete hematological response is observed at 16 weeks and maintained afterwards, the patient will be withdrawn from the study.
- In patients achieving complete response without transfusion support for a minimum of 8 weeks, the dose of eltrombopag may be reduced by 50%, and discontinued if counts remain stable after 8 weeks at the reduced dose. If relapse occurs after eltrombopag discontinuation, eltrombopag can be reintroduced at the last effective dosage.
- If new clonal cytogenetic abnormalities associated with dysplastic bone marrow findings are observed such as monosomy 7, eltrombopag should be permanently discontinued.

- If the patient develops myelodysplastic syndrome (MDS) or acute myeloid leukemia (AML) assessed by sensitive methods, eltrombopag will be permanently discontinued.
- If other non-clonal and/or cytogenetic abnormalities with uncertain meaning not previously observed and not associated with worsening blood counts or bone marrow dysplastic, the decision of discontinuing eltrombopag is up to the investigator, based on a more frequent bone marrow aspirate monitoring of cytogenetic abnormalities and dysplastic findings.
- If relapse of previous hematological disease occurs, eltrombopag will be permanently discontinued.
- If patient receives a new HSCT, eltrombopag will be permanently discontinued

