10.5.1 Other efficacy objective(s)

- To determine the response in each haematological lineage separately, the absolute frequency and valid percentage of patients who have a response in the neutrophil, platelet, and Hb lineages separately after 16, 24 and 36 weeks of eltrombopag, will be presented with the 95% CI. Descriptive statistics will also be provided between baseline and weeks 16, 24 and 36 for ANC, platelets and hemoglobin levels, and the appropriate paired exploratory tests will be done according to the type of distribution (parametric or not) to assess the statistical significance of the changes.
- To evaluate the overall hematological response rate (partial and complete) at 24 and 36 weeks after the initiation of eltrombopag, the frequency and percentage distribution and the corresponding 95% CI will be provided. This CI will be constructed as for the primary efficacy endpoint. Descriptive statistics will also be provided between baseline and week 24 and week 36 for ANC, platelets count and hemoglobin levels, and the appropriate paired exploratory tests will be done according to the type of distribution (parametric or not) to assess the statistical significance of the changes.
- To evaluate transfusion independence, the percentage of patients who were previously transfusion-dependent and do no longer require a RBC or platelet transfusion before and after the first 16 weeks of treatment will be calculated along with the 95% CI. This CI will be constructed as for the primary efficacy endpoint. The period where patients did not receive any platelet or RBC transfusions during the treatment period and follow-up will also be analyzed.

- To evaluate the discontinuation or reduction of concomitant G-CSF and/or EPO therapy, the percentage of patients who discontinue or reduce by $\geq 50\%$ from baseline the use of concomitant G-CSF and/or EPO therapy will be calculated along with the 95% CI. This CI will be constructed as for the primary efficacy endpoint.
- Overall survival, defined as the duration from inclusion in the study to date of death (whatever the cause), will be estimated with the Kaplan-Meier curves method and two-sided 95% CI for the estimated median. All patients who discontinue from the study, regardless the reason of discontinuation, will be followed for survival for 24 and 36 weeks, unless they withdraw their consent, die or are lost-to follow-up, in which case will be censored at the last contact.

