## 2.2 Study Design

This study is designed as an open-label, single-arm phase II study, in which patients diagnosed with primary or secondary PGF after allo-HSCT will be treated with eltrombopag up to week 36 or until the patient's premature withdrawal. If patient terminates eltrombopag for any of the reasons established in the withdrawal criteria, he/she will be followed for safety up to 30 days after the last dose of eltrombopag, unless he/she withdraws the consent, dies or is lost-to follow-up.

The primary efficacy endpoint is the overall hematologic response rate (partial and complete) by 16 weeks after the initiation of eltrombopag. Eltrombopag will be initiated on day 1 at a dose of 150 mg once daily (75 mg daily in Asian ancestry patients) and will be continued up to 36 weeks.

The study will consist of the following periods:

- Screening Period (baseline): the patient will be invited to participate in the study, after being informed of its characteristics. The patient screening criteria will then be reviewed, and the procedures established in the evaluation schedule will be performed.
- Treatment Period: from administration of the first dose of eltrombopag until time when patient permanently stops taking study treatment for any reason or until 36 weeks have passed.
  - Only patients with a partial or complete response at week 16 will continue to receive eltrombopag until loss of response (defined as a decrease in blood counts to levels that do not continue to meet the criteria for response established in this protocol), unacceptable toxicity, or discontinuation for any other reason.
  - Patients who discontinue eltrombopag because efficacy, will continue in the study and attend the scheduled visits of Treatment Period as per protocol. If loss of response occurs, eltrombopag will be reintroduced at the last effective dose.
- During the Treatment Period, patients will be evaluated weekly during the first month, every 2 weeks during the next 2 months and subsequently every 4 weeks until week 24. For the last 3 months, patients will be followed every 6 weeks.
- Final Visit (or Early Withdrawal): this visit will take place 30 days after completion of the Treatment Period, or premature patient withdrawal.

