## 4 ANALYSIS POPULATIONS

The populations that will be included in the analysis are defined below:

- The Full Analysis Set (FAS) comprises all patients to whom study treatment has been assigned. All analysis described in this document, except of AEs analysis (section 9) will be performed with this population.
- The Safety Set (SS) includes all patients who received at least one dose of study treatment. Only AEs analysis (section 9) will be performed with this population.
- Per-Protocol Set (PPS) consists of a subset of the patients in the FAS who are compliant with requirements of the clinical study protocol.

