**To evaluate the transfusion independence for red blood cells (RBC) and/or platelets after the initiation of eltrombopag.**

It will be calculated:

- The patient receive at least one transfusion before start treatment (No / Yes) (data in section “Supportive Care Record”).
- The patient receive at least one transfusion after start treatment and before week 16 (No / Yes) (data in section “Supportive Care Record”).
- The patient receive at least one transfusion after week 16 and before end treatment (No / Yes) (data in section “Supportive Care Record”).

In each of the studied moments, it will be shown the number of transfusions per patient. In addition, for total of transfusions, it will be shown the type of transfusion (Platelets / RBC).

It will be performed:

- Analysis of contingency tables between number of patients with transfusions before start treatment and before week 16, using chi-square or Fisher's exact test.
- Analysis of contingency tables between number of patients with transfusions before start treatment and after week 16, using chi-square or Fisher's exact test.

It will be calculated:

- The period of time where patients did not receive any platelet or RBC transfusions during the treatment period, calculated as the difference between the number of days in treatment and the number of days with transfusions.

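### SAP 10.4's after-week-16 transfusion flag has essentially no observation time for patients already off drug by week 16, and no rule says how to score them

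*SAP*

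**What the plan says.** SAP 10.4 (Secondary objective 3) splits transfusion history into three windows: before treatment, from treatment start to week 16, and a late window. The middle item is "The patient receive at least one transfusion after start treatment and before week 16 (No / Yes") and the late item is "The patient receive at least one transfusion after week 16 and before end treatment (No / Yes"). Only the late item is cut off by the end of treatment. It is then compared with pre-treatment status: "Analysis of contingency tables between number of patients with transfusions before start treatment and after week 16, using chi-square or Fisher's exact test".

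SAP 4 puts this on the full analysis set: "All analysis described in this document, except of AEs analysis (section 9) will be performed with this population". SAP 3 reports percentages both with and without missing values in the denominator.

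Two places decide who has time in the late window. Protocol 6.1.2 states: "If no partial or complete hematological response is observed at 16 weeks and maintained afterwards, the patient will be withdrawn from the study". SAP 2.2 states: "Only patients with a partial or complete response at week 16 will continue to receive eltrombopag until loss of response", and runs the treatment period "until time when patient permanently stops taking study treatment for any reason or until 36 weeks have passed".

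Protocol 10.5.1 defines the endpoint as a percentage with a 95% CI. The group it counts is, in its wording: "previously transfusion-dependent and do no longer require a RBC or platelet transfusion before and after the first 16 weeks of treatment". The same bullet analyses the transfusion-free period over both treatment and follow-up.

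**The concern.** A patient permanently off drug at or before week 16 has no stretch of time that is both after week 16 and before end of treatment. No transfusion, however many are given, can turn that patient's late flag to 'Yes'. A 'No' then records only that the patient is off drug, yet it reads as freedom from transfusion.

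The patients affected are mainly those who did not respond. Under literal coding the distortion therefore favours the drug, and it grows as the response rate falls. Under missing coding these patients leave the valid percentage, and what remains is close to a rate among responders. Either way, the figure reported for a stated secondary objective would not answer the protocol's question.

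Equal window lengths or a paired test would not cure this, because the affected patients would still carry an uninformative 'No'.

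**Working it through.** **Inputs.** N = 33 and 45% response (Protocol 10.7); full analysis set (SAP 4); non-responders leave treatment at week 16 (Protocol 6.1.2, SAP 2.2). The documents give no figure for baseline transfusion dependence or for late transfusion freedom, so both are assumed below.

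**The plan's own figure.** No figure is stated for transfusion independence. The design figure reproduces: the one-sided exact lower limit at x = 0.45 × 33 = 14.85 is 30.08%, against the stated 30.1%. In whole patients, 45% is about 15 responders and 33 − 15 = 18 non-responders.

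**Empty windows.** About 18/33 = 54.5% of patients have essentially no late window at the planned response. This is approximate. The week-16 visit has a window of ±3 days (Protocol 7.1), and response needs two tests at least 7 days apart (Protocol 7.3.1.1), so a few may have some days of treatment after week 16.

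**Three codings.** Assume all 33 were previously dependent, 15 continue past week 16, 18 have an empty window, and k of the 15 are transfusion-free afterwards.

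- Coded 'No': (18 + k)/33
- Excluded (valid percentage): k/15
- Counted as not independent: k/33

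| k | Coded 'No' | Excluded | Not independent |
|---|---|---|---|
| 0 | 18/33 = 54.5% | 0/15 = 0% | 0/33 = 0% |
| 8 | 26/33 = 78.8% | 8/15 = 53.3% | 8/33 = 24.2% |
| 12 | 30/33 = 90.9% | 12/15 = 80.0% | 12/33 = 36.4% |
| 15 | 33/33 = 100% | 15/15 = 100% | 15/33 = 45.5% |

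The gap between the first and last codings is 18/33 = 54.5 points at every k. With 5 empty windows it is 5/33 = 15 points, and with 20 it is 20/33 = 61 points.

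**An extreme case, for scale only.** Suppose 28 of 33 were transfused before treatment, split evenly by response (28 × 15/33 ≈ 13 among responders), and all 13 are still transfused later. With 'No' coding the table compares 28/33 with 13/33: Fisher p = 0.0003. An exact McNemar test on the 15 discordant patients gives 2 × 0.5^15 = 0.00006. With 22 responders (67%) and 24 transfused beforehand, the comparison is 24/33 with 16/33 and Fisher p = 0.08.

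**Can data after end of treatment fill the gap?** In part. Supportive care is recorded at the Final Visit, 30 days after the last dose (Protocol 7.2.3), but the SAP window ends before it. For a patient stopping at week 16, that visit would cover about 30 days after week 16. For a patient whose last dose was more than 30 days before week 16, the visit also falls before week 16.

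**The case against.** The strongest reply is that no sentence in the SAP tells the analyst to score these patients 'No'. The item has two levels and no rule for a patient with no time at risk, and SAP 3 provides for missing values, so exclusion is equally open. This stands. A reader might infer that the SAP prescribes a favourable score; it does not. It leaves the choice open between two codings, neither of which gives the protocol's percentage.

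A reader might also infer that everyone with an empty window is a treatment failure. SAP 10.1 counts a patient who leaves before week 16 with a response at the last evaluation as a responder. Such patients have an empty window too, and scoring them as not independent without comment would sit awkwardly beside the primary analysis. A temporary interruption is also not an end of treatment.

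A third tempting reading is that the comparison will reach significance with no benefit at all. The extreme case does not support that as an expectation. Platelet and hemoglobin partial responses require independence from the corresponding transfusion (Protocol 7.3.1.1). For every previously transfused responder to remain transfused, each would have to respond on neutrophils alone, or be free of one product while still receiving the other. The result also loses significance on Fisher's test at 67% response with 24 transfused beforehand.

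Finally, the reach is limited. This is one of three windows for an unpowered secondary objective. The before-week-16 flag is unaffected, and SAP 8 reports how many patients stop at week 16 for lack of response. SAP 10.4 does not itself compute an independence rate. That last point does not rescue it: the flags and their tables are what it offers in place of the protocol's percentage and CI.

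**Conclusion.** The point holds as a missing scoring rule and denominator. The late flag is uninformative for about 18 of 33 patients at the planned response, less any with a few days of treatment after week 16. Literal coding inflates apparent transfusion freedom. Missing coding gives something close to a responder-only rate. Neither is the endpoint in Protocol 10.5.1.

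The illustrative spread of 91%, 80% and 36% rests on two assumptions that the documents do not supply: all 33 previously dependent, and 12 of 15 responders transfusion-free. The direction does not rest on them. 'No' coding exceeds the not-independent coding whenever any window is empty, and exclusion exceeds it whenever at least one continuing patient is transfusion-free and at least one window is empty.

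The documents do not support saying that the SAP mandates 'No', that all affected patients are failures, or that a spurious significant result is to be expected. The change should be made before analysis, but the primary endpoint is untouched.

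**What to change.** In SAP 10.4:

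1. Use previously transfusion-dependent patients in the full analysis set as the denominator, and report the protocol's percentage with its CI.
2. Do not code an empty late window as 'No'. In the main analysis, count patients with no treatment time after week 16 as not shown to be transfusion independent after week 16.
3. Report the number of such patients. Show early-exit responders (SAP 10.1) as a separate line and vary their scoring in a sensitivity analysis.
4. Report the rate among patients still on treatment after week 16, with its n, as supportive only.
5. Use the supportive-care data already recorded at the Final Visit, in line with the protocol's inclusion of follow-up in the transfusion-free period. State that these data reach past week 16 only for patients whose last dose was less than 30 days before it, or later.

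The cost is one derivation rule, using treatment dates that SAP 8 already needs, and a less favourable reported rate. No new data collection is required.

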### **3 STATISTICAL METHODS**

Quantitative variables are described with measures of central tendency and dispersion: mean, median, SD, Q1, Q3, minimum and maximum).

Qualitative variables are described using absolute and relative frequencies (N, %). Two percentage columns are presented, total percentage (total %) and valid percentage (valid %), that is, the percentage over the sum of valid responses plus missing values and the percentage over the total of valid responses. When there are not missing values both of them are equal, and then only one will be show.

[figure not shown]
In the analysis of contingency tables as well as for the comparison of proportions and / or frequency distributions, the chi-square test (or Fisher's exact when appropriate) will be used.

For dependent samples, parametric (t-test paired) or non-parametric (Wilcoxon) statistical tests will be performed depending on the distribution of the sample.

The "time to event" variables (overall survival) will be analyzed using the Kaplan-Meier method.

These tests will be used in all bilateral cases and with a level of significance of 0.05. In cases where a p-value less than 0.05 appears, it refers to the existence of statistical significance.

Data will be analyzed using SPSS v22.0.

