#### **10.5 Secondary objective 4**

##### **To evaluate the reduction and discontinuation of concomitant granulocyte colony-stimulating factor (G-CSF) and/or erythropoietin (EPO) therapy.**

It will be calculated:

- The patient receive EPO at start of treatment (No / Yes) (data in section "Supportive Care Record").
- The patient receive EPO in visit 6, visit 9, visit 11, visit 13, visit 15 and visit 16 (No / Yes) (data in section "Supportive Care Record").
- The patient reduce EPO at least 50% from start of treatment to visit 6, visit 9, visit 11, visit 13, visit 15 and visit 16 (No/ Yes) (data in section "Supportive Care Record").
- The patient receive G-CSF at start of treatment (No / Yes) (data in section "Supportive Care Record").
- The patient receive G-CSF in visit 6, visit 9, visit 11, visit 13, visit 15 and visit 16 (No / Yes) (data in section "Supportive Care Record").
- The patient reduce G-CSF at least 50% from start of treatment to visit 6, visit 9, visit 11, visit 13, visit 15 and visit 16 (No / Yes) (data in section "Supportive Care Record").

It will be realized:

- Analysis of contingency tables between number of patients who receive EPO at start of treatment and in visit 6, visit 9, visit 11, visit 13, visit 15 and visit 16, using chi-square or Fisher's exact test.
- Analysis of contingency tables between number of patients who receive G-CSF at start of treatment and in visit 6, visit 9, visit 11, visit 13, visit 15 and visit 16, using chi-square or Fisher's exact test.

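### SAP 10.4 and 10.5 test before/after status in the same patients with unpaired chi-square or Fisher tests, and SAP 10.4 drops the follow-up that protocol 10.5.1 includes in the transfusion-free period

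*SAP*

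**What the plan says.** **Tests.** For secondary objective 3, SAP 10.4 records whether each patient had at least one transfusion before treatment, between treatment start and week 16, and between week 16 and the end of treatment. It then plans "Analysis of contingency tables between number of patients with transfusions before start treatment and before week 16, using chi-square" or Fisher's exact test, and repeats this for the period after week 16. For secondary objective 4, SAP 10.5 plans "Analysis of contingency tables between number of patients who receive EPO at start of treatment and in visit 6" and at visits 9, 11, 13, 15 and 16, again with chi-square or Fisher, and the same for G-CSF.

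SAP section 3 covers paired data with one sentence: "For dependent samples, parametric (t-test paired) or non-parametric (Wilcoxon) statistical tests will be performed depending on the distribution of the sample". Those are tests for quantitative variables. The same section assigns chi-square or Fisher to contingency tables and to comparisons of proportions. It adds: "In cases where a p-value less than 0.05 appears, it refers to the existence of statistical significance".

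Protocol 10.5.1 plans no test for either objective. For transfusions it asks for one quantity, with a 95% CI: "percentage of patients who were previously transfusion-dependent and do no longer require a RBC or platelet transfusion before and after the first 16 weeks". For G-CSF and EPO it asks for the percentage who stop or at least halve use, also with a 95% CI.

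**Transfusion-free period.** Protocol 10.5.1 states: "The period where patients did not receive any platelet or RBC transfusions during the treatment period and follow-up will also be analyzed". SAP 10.4 restricts this to the treatment period, "calculated as the difference between the number of days in treatment and the number of days with transfusions".

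**The concern.** With one arm, every comparison of start with a later period is within patient. A valid test of change must use the patients whose status changed. A chi-square or Fisher test does not do that, whichever way the table is built. Because SAP section 3 treats any p-value below 0.05 as statistical significance and gives these tests no exploratory label, their results could be reported as evidence for or against an effect on transfusion or growth-factor use.

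On the time measure, patients who stop eltrombopag because it has worked stay in the study and attend the scheduled visits (protocol 4.1). Transfusion need is monitored at each visit (protocol 7.3.1.2), and supportive care is listed at the Final Visit (protocol 7.2.3). A measure confined to treatment discards transfusion-free time that was observed and that the protocol asked for.

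**Working it through.** The plan gives no figure of its own for these analyses, so there is none to reproduce. From the documents: planned n=33 (SAP 2.2), two-sided 0.05 level (SAP 3), two later periods (SAP 10.4), six visits for each of EPO and G-CSF (SAP 10.5). **All cell counts below are assumptions**, chosen to show how the tests behave.

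**1. Number of tests.** 2 + 6 + 6 = 14, if each later period or visit is compared with the start.

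**2. Reference test.** Exact McNemar uses only the discordant pairs. With b patients stopping and c starting, it refers min(b, c) to a Binomial(b + c, 0.5). For six stopping and none starting, p = 2 × 0.5^6 = 0.031.

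**3. Layout A, before-by-after cross-tabulation.** Rows are before yes/no, columns after yes/no, one count per patient. The null hypothesis is that later status is independent of earlier status, which is not the hypothesis of no change.

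| Assumed case | Table | Fisher | Exact McNemar |
|---|---|---|---|
| EPO, 6 users, nobody stops | [6,0],[0,27] | 0.0000009 | 1 (no discordant pairs) |
| EPO, 6 users, all stop | [0,6],[0,27] | 1 | 0.031 |
| Transfusion, no net change | [20,3],[3,7] | 0.002 | 1 |
| Transfusion, 28 before, 20 become free | [8,20],[0,5] | 0.30 | 0.000002 |

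The p-value is small when patients keep their status and large when users stop. If all 33 were transfused before treatment, the table has an empty row: chi-square cannot be computed and Fisher returns 1 whatever happens later.

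**4. Layout B, stacked by period.** The rows are the two periods, so the test does compare proportions, but it treats 66 records from 33 patients as independent. In each case below six stop and none start, so McNemar p=0.031 throughout.

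| Before v after | Stacked Fisher |
|---|---|
| 18 v 12 of 33 | 0.22 |
| 33 v 27 of 33 | 0.024 |
| 15 v 9 of 15 | 0.017 |

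The same change within patients gives p-values on both sides of 0.031. The error has no fixed direction.

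**5. Transfusion-free period.**
- Protocol Table 7-1 puts week 36 at Day 253 and the Final Visit at Day 283: 283 − 253 = 30 days. These are lost to a patient treated to week 36, on any reading of the SAP formula.
- If days in treatment means drug start to drug end, as SAP section 8 defines duration of treatment, more is lost. Under protocol 6.1.2 a complete responder from week 8 can have the dose reduced at week 16 (8 + 8) and stop at week 24 (16 + 8). With no restart and no transfusion, the score is 24 × 7 = 168 days. Week 36 is 36 × 7 = 252 days, so 252 − 168 = 84 observed days are lost to week 36.

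**The case against.** **The layout may be stacked.** SAP 10.4 speaks of numbers of patients in each period, and SAP section 3 gives chi-square for comparing proportions, so stacking is a natural reading. On that reading the four cases in step 3 give p=1 (6 v 6 of 33), 0.024 (6 v 0), 1 (23 v 23) and 0.0000013 (28 v 8), all agreeing with McNemar at 0.05. This stands. A reader might infer that the planned tests will report results the wrong way round. The documents do not support that in general, because it follows only from the cross-tabulated layout. What remains for the stacked layout is a p-value that ignores pairing. It changes the conclusion in one of the three stacked examples (0.22 against 0.031).

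**The counts are invented.** True. The case of 20 patients needing no transfusion at all from Day 1 is also optimistic, since entry requires platelets below 20,000/µL. The examples show what the tests respond to; they are not forecasts.

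**Efficacy stoppers may still be in the treatment period.** Protocol 4.1 has them attending that period's visits, with possible restart. If their days count as days in treatment, only the roughly 30 days to the Final Visit are lost. This stands, so 84 days is the figure for one reading. A reader might also infer that the measure ranks a good responder (168 days) below a patient transfused weekly for 36 weeks (252 − 36 = 216 days). That needs the same reading, the earliest optional taper, and a patient kept on drug by a neutrophil-only response. It is possible but extreme.

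**Total transfusion-free days is a legitimate measure.** The protocol does not ask for the longest interval, and frequent transfusion would be visible elsewhere: "In each of the studied moments, it will be shown the number of transfusions per patient". This stands.

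**The protocol's percentages are not lost.** A reader might infer that the SAP drops them. It does not: yes/no counts, total and valid percentages and 95% CIs supply most of what is needed.

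**McNemar has limits here.** After week 16 it would cover mainly responders, because only they continue on drug. The windows also differ: protocol 6.3 records transfusions for the 30 days before entry, against 16 weeks or more afterwards. Both points stand and argue for deleting the tests.

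**Conclusion.** The concern holds on two points, and both should be fixed.

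First, the chi-square/Fisher comparisons in SAP 10.4 and 10.5 are invalid for paired data in either layout. Cross-tabulated, they test association: with assumed counts, p=0.0000009 when no EPO user stops and p=1 when all six do. Stacked, they address change but with a p-value that is off in either direction (0.22 or 0.024 where exact McNemar gives 0.031). They also go beyond protocol 10.5.1, which plans percentages with CIs only.

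Second, SAP 10.4 narrows the transfusion-free period without explanation. The loss is about 30 days for a patient treated to week 36, and up to 84 days to week 36 for a patient who stops for efficacy at week 24 if days in treatment means drug start to drug end. The protocol does not define follow-up for transfusions; reading it as extending to the Final Visit is an assumption, supported by the supportive-care entry there and by SAP 10.5's use of visit 16.

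These are secondary analyses. The primary endpoint and the sample-size rationale are unaffected.

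**What to change.** 1. Delete the chi-square and Fisher comparisons in SAP 10.4 and 10.5. Report the protocol 10.5.1 percentages with 95% CIs among patients transfused, or on EPO or G-CSF, at baseline.
2. If a test is kept, use exact McNemar on patients with both assessments, add it to SAP section 3 as the paired test for binary data, and label it exploratory. State beside it that after week 16 it covers mainly responders and that the before and after windows differ in length.
3. In SAP 10.4, run the transfusion-free period from Day 1 to the last visit with supportive-care recording, up to the Final Visit and including time after stopping for efficacy. Report each patient's observation time beside it.

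The cost is SAP wording and some reprogramming from supportive-care data already collected. No new data or visits are needed.
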